6.12 Appropriateness of Measurements

All PK, PD, and safety assessments are typical of those that are usually employed in studies aiming to establish a PK/PD relationship. When available, appropriate standard guidelines will be used.

We and others have previously demonstrated that the density of $\alpha_v \beta_6$ integrin receptor can be measured utilizing PET probes in IPF patients. The evaluation of receptor occupancy of an investigational compound with PET imaging has been a well-established method in the study of neurological receptors for many years. We are applying both approaches to evaluate the PK/PD relationship of PLN-74809 in IPF patients. Assessment of the primary endpoint will be made using standard methods for quantifying the amount of PET tracer bound to the $\alpha_v \beta_6$ integrin receptor in the lungs before and after administration of study drug. Standard mathematical and analytical tools will be used to determine if the presence of PLN-74809 reduces the binding of the PET tracer. Tracer uptake before and after treatment will be quantified to estimate changes in receptor density.

Confidential Page 313 of 331

Pliant Therapeutics Inc.
Page 39

7 STUDY ACTIVITIES

The Schedule of Events with study activities is provided in Appendix 1.

| When multiple study procedures are scheduled at the sa | ame time point, the suggested order of | | |
|---|---|--|--|
| procedures is as follows but may be adjusted by the site | e staff to allow flexibility in the study | | |
| flow: obtain vital signs, collect urine san | nple, and collect blood sample. When | | |
| several assessments are required at the same time point, evaluations should be completed so | | | |
| that the PK sample is collected at the required time. | | | |
| | | | |

When samples

for PK purposes are scheduled for collection around a PET procedure, the PK samples should be obtained as close as possible to the prescheduled timing while minimizing interference with the PET procedure, which has priority.

Confidential Page 314 of 331

8 QUALITY CONTROL AND ASSURANCE

During the study, the Sponsor and/or representatives of the Sponsor may visit the site to conduct an audit of the study. The purpose of this visit will be to determine the Investigator's adherence to the protocol, applicable regulations, and the Sponsor's procedures, in addition to assessing the accuracy of the study data. Prior to initiating this audit, the Investigator will be contacted by the Sponsor to arrange a convenient time for this visit. The Investigator and staff are expected to cooperate with the auditors and allow access to all participant records supporting the eCRFs and other study-related documents.

At some point during the development program for the study drug, a regulatory authority may visit the Investigator to conduct an inspection of the study and the site. The Investigator and staff are expected to cooperate with the inspectors and allow access to all source documents supporting the eCRFs and other study related documents. The Investigator must immediately notify the Sponsor when contacted by any regulatory authority for purposes of conducting an inspection.

Confidential Page 315 of 331

9 PLANNED STATISTICAL METHODS

9.1 General Considerations

This is an exploratory study; as such, no statistical hypotheses are being tested. In general, data will be summarized using statistical summary methods; graphic presentations of data may also be prepared. The contract research organization (CRO) will be responsible for the preparation of tables and listings and will assist in the preparation of figures, which may be done by Sponsor personnel. A statistical analysis plan (SAP), prepared and agreed before final database lock, will describe the analytic approach and methods in more detail.

9.2 Determination of Sample Size

The sample size has been set empirically. Up to 12 participants should provide proof of concept on the ability of the study to assess target engagement ($\alpha_v\beta_6$ receptor occupancy by PLN-74809). Pharmacodynamic, PK, and safety/tolerability evaluation of PLN-74809 will be assessed in the target population.

9.3 Analysis Populations

Safety Population: All participants who receive one dose of study drug will be included in the Safety Population.

PET Population: All participants with at least a baseline PET will be included in the PET Population.

PK Concentration Population: All participants who receive one dose of study drug and have any measurable PLN-74809 concentration data will be included in PK Concentration Population.

PK Analysis Population: All participants who have sufficient PLN-74809 concentration data for PK calculation will be included in the PK Analysis Population.

9.4 Pharmacokinetic Analysis

Plasma PLN-74809 concentrations at each sampling time point will be presented in listings and summarized with descriptive statistics. Plasma PLN-74809-versus-time profiles (with plasma concentrations on both a log and linear scale) will be plotted for each participant.

Non-compartmental analysis will be used to calculate the PK parameters T_{max} , C_{max} , area under the drug concentration-time curve from time zero to the time of the last measurable concentration (AUC_{last}), AUC from time zero to 4 hours (AUC₍₀₋₄₎) and from time zero to 24 hours (AUC₍₀₋₂₄₎) after dosing, and average drug concentration (C_{avg}), if applicable. Plasma PK parameters will be presented in listings and summarized with descriptive

Confidential Page 316 of 331

statistics. Further details of the analyses will be provided in the SAP, which will be prepared and agreed prior to final database lock at the end of the study. The PK analysis plan and report may be prepared separately from the SAP, as appropriate.

9.5 Pharmacodynamic Analysis

9.5.1 α_νβ₆ Receptor Occupancy from PET Imaging

PET-CT scans will be interpreted by American Board of Nuclear Medicine (ABNM)-certified nuclear medicine physicians in an unblinded manner. Lung contours will be generated from Baseline and post-treatment PET-CTs. Mean and maximum standardized uptake value (SUV) measurements of contoured lungs will be calculated using MIMS software, by analyzing the uptake values of [18F]FP-R₀1-MG-F2 within the lung, and comparing values from the Baseline and post-treatment scans. Numerical and graphical results will be presented by dose.

In addition, relationships between PK and PET receptor occupancy, as well as between HRCT and PET receptor imaging, may be evaluated in an exploratory fashion and presented in a graphical manner.

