2 STUDY OBJECTIVES

The primary objective of this study is:

• Evaluation of $\alpha_v \beta_6$ receptor occupancy by PLN-74809 in the lungs, as assessed by changes from baseline in $\alpha_v \beta_6$ PET tracer uptake patterns following a single dose.

The secondary objective is:

• Assessment of the safety and tolerability of PLN-74809 in IPF participants

The exploratory objective is:

•

Confidential Page 294 of 331

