6.9 Pharmacodynamic Assessments

6.9.1 PET Imaging

All PET imaging will be performed at prespecified times according to the Schedule of Events (see Appendix 1), using the R₀1 Knottin tracer as synthetized by the Radiology Department at Stanford Medical Center, and following predefined instructions as detailed in the study Radiology Manual.

PET imaging that is performed following administration of PLN-74809 on Day 1 will be conducted as much as possible to coincide with PLN-74809 T_{max} (at least 4 hours post-dose and no more than 30 minutes after the 4 hour PK timepoint) to assess $\alpha_v \beta_6$ receptor occupancy.

Blood samples for radiotracer PK will be obtained at the following time points: 1, 3, 5, 10, 30, and 60 minutes after completion of radiotracer injection for PET-computed tomography (CT) to obtain blood time activity measurements. Each collection time point has a +4-minute window. During some PET-CT scans, sample collection may not be possible or may be obviated due to staffing availability or scientific considerations. Refer to the Radiology Manual for details, including definitive information regarding the allowed sample collection windows.

Confidential Page 307 of 331

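### The only PET analysis stated for the receptor-occupancy objective is a before/after comparison of whole-lung SUV, whose percentage change is not percentage occupancy, and no stated analysis uses the tracer blood samples

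*Protocol*

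**What the plan says.** Protocol section 2 sets receptor occupancy in the lungs as the primary objective, to be assessed from change in "PET tracer uptake patterns following a single dose". The SAP (3.1) makes the change in uptake patterns the primary endpoint.

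The one stated PET analysis is Protocol 9.5.1, repeated in the Synopsis. "Mean and maximum standardized uptake value (SUV) measurements of contoured lungs will be calculated using MIMS software", and the analysis consists of "comparing values from the Baseline and post-treatment scans", presented by dose. The section is headed as receptor occupancy, and its optional exploratory part speaks of "relationships between PK and PET receptor occupancy". The visible text gives no occupancy formula, reference region, blood normalisation, estimate of non-displaceable uptake or kinetic model.

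Protocol 6.12 is general: "Standard mathematical and analytical tools will be used to determine if the presence of PLN-74809 reduces the binding of the PET tracer". It then adds: "Tracer uptake before and after treatment will be quantified to estimate changes in receptor density".

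Protocol 6.9.1 provides for tracer blood: "Blood samples for radiotracer PK will be obtained at the following time points: 1, 3, 5, 10, 30, and 60 minutes" after injection, for the purpose of a blood time-activity curve. It also warns that at some scans "sample collection may not be possible or may be obviated due to staffing availability or scientific considerations". The pharmacokinetic analyses in Protocol 9.4 and SAP 6.10 cover PLN-74809 only, so no visible analysis uses the tracer blood data.

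The SAP (sections 1, 2.1, 3.1 and 6.2.8) leaves PET analysis to a separate plan that is not among the documents.

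**The concern.** Tracer signal in a lung contour is the sum of specific binding to αvβ6, non-specific (non-displaceable) uptake and tracer still in blood. A competing drug lowers only the specific part. A percentage fall in SUV is therefore occupancy scaled by the specific share of the baseline signal, and shifted by any difference in tracer delivery between the two scans.

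This matters because the trial exists to relate dose and exposure to occupancy. The specific share may differ between participants, and up to 12 participants are spread over five dose labels (SAP 6.3.1). By-dose SUV changes read as occupancy could then partly reflect who was scanned at each dose. The blood samples could remove the delivery part of the problem, but no stated analysis takes them up.

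The wording in 6.12 adds to the confusion. A competitive drug changes how much tracer binds, and a fall in tracer binding after one dose is not evidence of a change in receptor density.

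**Working it through.** **Figure in the plan.** No power or precision figure bears on this point: the sample size is empirical and no hypothesis is tested (Protocol 9.1 and 9.2). The related figure is tracer blood volume in Appendix 3. Six time points × 2 scans = 12 samples, and 12 × 3 mL = 36 mL, which agrees with the table. With the permitted maximum of 3 scans, full sampling would be 6 × 3 = 18 samples and 54 mL, so the table covers two scans.

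**Model.** Set baseline lung SUV to 1 and define:
- s: specific share of baseline SUV. Not in the documents; assumed 0.5 to 0.9.
- 1 − s: non-displaceable plus blood share, hence 0.5 to 0.1.
- r: post-dose/baseline ratio of tracer delivery, scaling the whole lung signal. Not in the documents; assumed 0.8 to 1.2.
- O: true occupancy.

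Post-dose SUV = r × [(1 − s) + s(1 − O)] = r × (1 − sO).

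Apparent fall = 1 − r(1 − sO).

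**Step 1: unchanged delivery (r = 1).** The apparent fall is s × O.

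| True occupancy | s = 0.9 | s = 0.7 | s = 0.5 |
|---|---|---|---|
| 90% | 81% | 63% | 45% |
| 50% | 45% | 35% | 25% |

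**Step 2: no occupancy, changed delivery (O = 0).** The apparent fall is 1 − r: +20% at r = 0.8 and −20% at r = 1.2.

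**Step 3: both together.**
- O = 0.5, s = 0.9, r = 0.8: 1 − 0.8 × (1 − 0.45) = 56%, above the true 50%.
- O = 0.5, s = 0.5, r = 1.2: 1 − 1.2 × (1 − 0.25) = 10%, far below it.

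The direction of the error is therefore not fixed.

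**Step 4: what blood data can repair.** Dividing each scan by its blood activity removes r in this model. True occupancy of 50% then reads 45%, 35% or 25% for s = 0.9, 0.7 or 0.5, whatever r was. The scaling by s remains. Only a further step that also removes the non-displaceable part, dividing by s here, returns 50%.

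**The case against.** The strongest reply is that the PET analysis is not in these documents. The SAP says repeatedly that a separate plan will hold it, and 6.12 promises standard quantification methods. A reader might infer that raw SUV is all that will be done, but the documents do not support that. What stands is that the protocol's own analysis section names only SUV, and that the visible list of changes in SAP section 9 alters populations and not the PET measure.

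Second, the SAP endpoint is change in uptake, which a paired SUV comparison measures directly, and the study seeks proof of concept without hypothesis tests. This is fair: SUV change can show the direction of target engagement. The difficulty begins when the percentage is read as occupancy or compared across doses on that footing. Even then, if a participant's specific share is stable and delivery is unchanged, the ordering of two doses within that participant survives.

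Three stronger readings are tempting:
- That SUV must understate occupancy. This holds with unchanged or increased delivery, but a fall in delivery can push the reading above the truth.
- That the distortion is extreme. A specific share of 0.3 with a 20% rise in delivery makes 90% occupancy read as about 12% and 50% as −2%. The arithmetic is right, but it joins two unfavourable assumptions, and nothing in the documents makes them likely.
- That the +4-minute windows spoil the early blood samples. The 1-, 3- and 5-minute windows do overlap, but 6.9.1 refers to the Radiology Manual, not provided, for the definitive windows.

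It is also fair to object that blood samples alone do not yield occupancy, as step 4 shows.

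**Conclusion.** The concern holds in a limited form. As far as the protocol and SAP state it, the occupancy objective rests on a whole-lung SUV comparison, with no stated rule for turning that change into occupancy and no stated use of the tracer blood curve. That the percentage fall is not percentage occupancy follows from what SUV contains and needs no outside figure.

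The size does need assumptions. For a specific share of 0.5 to 0.9 and unchanged delivery, 90% occupancy reads as 45% to 81%. A 20% change in delivery alone shifts the reading by about 20 points in either direction at zero occupancy. The documents supply neither input, so these figures show sensitivity and do not predict the error in this trial.

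The conclusion is conditional on the separate PET plan. If it already defines an occupancy measure and uses the blood data, what remains is to bring 9.5.1 and 6.12 into line. The point deserves action in an exploratory study because it concerns the meaning of the primary result and is cheap to settle.

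**What to change.** In Protocol 9.5.1 and the separate PET plan:

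1. For each Baseline/post-dose pair, report blood-normalised uptake next to SUV. Use the lung-to-blood ratio from the samples already drawn, or an image-derived blood value if a blood pool lies in the field of view.
2. Call the SUV change *reduction in tracer uptake*.
3. Use *occupancy* only for a measure that also accounts for non-displaceable uptake. One option is to regress regional baseline-minus-post-dose uptake on regional baseline uptake, where the slope estimates occupancy. Another is a kinetic model. Either applies only where the scan data allow, since the visible text does not say whether scans are dynamic or blood is metabolite-corrected. For the regression, state the assumption that non-displaceable uptake is similar across lung regions.
4. State how many pairs have blood data at both scans and how the others are handled.

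In Protocol 6.12, replace *receptor density* with *tracer binding*.

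The cost is modest: wording and a little more analysis of material already collected. The downside is that pairs without blood data at both scans contribute only SUV or an image-derived value.

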9.5.2 FVC from Spirometry

FVC, percent of predicted and volume (mL), will be assessed using the standard spirometry procedure at the Chest Clinic at Stanford Medical Center and presented as absolute values and as percent of predicted values.

9.5.4 HRCT

Visual results will be presented in listings and summarized with descriptive statistics by dose to support the inclusion criteria. Quantitative volumetric HRCT results will be analyzed and presented individually and in relationship to the PET findings. Results will be presented in tabular and graphical form.

9.6 Safety Analysis

Safety data from all participants who receive one dose of study drug will be incorporated into the final safety analysis. Further details of the safety analyses will be provided in the SAP. AEs will be collected from the time the participant signs the ICF until the last study visit. AEs will be coded using the Medical Dictionary for Regulatory Activities (MedDRA®).

Confidential Page 317 of 331

All AEs will be listed by participant and summarized in a table. The incidence of AEs, the incidence of treatment-emergent AEs (TEAEs), the incidence of treatment-related AEs, and the severity of AEs will be summarized by system organ class (SOC), preferred term, and maximum severity. In cases in which a participant reports multiple occurrences of the same event (preferred term), the greatest severity will be included in the summary. The number and percentage of participants with SAEs and treatment-related SAEs and the number and percentage of participants who withdraw due to an AE will be tabulated.

Clinical laboratory test parameters will be listed, using the CTCAE grading scale, for individual participants, with values outside the reference ranges flagged. The incidence of treatment-emergent laboratory abnormalities will be summarized by severity. Summary statistics will be calculated for each parameter.

Vital sign measurements, other laboratory tests, concomitant medications, medical history and changes in physical examinations at each time point will be listed by participant.

Concomitant medications will be coded using the most current World Health Organization (WHO) drug dictionary available.

9.7

Confidential Page 318 of 331

10 ADMINISTRATIVE CONSIDERATIONS

10.1 Institutional Review Board Approval

It is the responsibility of the Investigator to assure that all aspects of the study are conducted in accordance with the Declaration of Helsinki as described in the International Council for Harmonisation (ICH) E6: Guideline for Good Clinical Practice (GCP), and/or local laws, whichever provides the greatest level of protection for the study participants. The protocol and any information supplied to the participant to obtain informed consent, including written ICF(s), participant recruitment procedures (e.g., advertisements), and written information to be provided to participants (information leaflets), must be reviewed and approved by a qualified IRB prior to enrollment of participants in the study. Prior to initiation of the study, the Sponsor must receive documentation of the IRB approval, which specifically identifies the study/protocol, and a list of the committee members.

Amendments to the protocol and revisions to the informed consent must also be submitted to and, if required, approved by the IRB.

The Investigator must submit progress reports to the IRB in accordance with the IRB requirements. Annual re-approval of the study must be obtained. Copies of progress reports and Annual re-approvals must be sent to the Sponsor.

When the Sponsor provides the Investigator with a safety report, the Investigator must promptly forward a copy to the IRB.

After completion or termination of the study, the Investigator must submit a final report to the IRB and to the Sponsor.

The Investigator, as part of the records retention requirements for the study, must maintain documentation of all submissions, correspondence, and approvals to and from the IRB.

Each clinical Investigator is responsible to conduct the study in accordance with the protocol, all applicable laws, regulations, and GCP according to ICH guidelines.

10.2 Ethical Conduct of the Study

The study will be carried out in accordance with the current version of the Declaration of Helsinki, concerning medical research in humans (recommendations guiding physicians in biomedical research involving human participants). The study will be conducted in adherence to the study protocol and GCPs, as defined in Title 21 of the US Code of Federal Regulations Parts 50, 54 56, and 312 and Part 11, as well as ICH E6: Guideline for Good Clinical Practice (ICH GCP) consolidated guidelines (E6) and applicable regulatory requirements.

10.3 Participant Information and Consent

Preparation of the ICF is the responsibility of the Investigator and the Sponsor or designee. It must include all elements required by the ICH, GCP, and applicable regulatory requirements

Confidential Page 319 of 331

and must adhere to GCP and to the ethical principles that have their origin in the Declaration of Helsinki.

The Sponsor or designee must review and approve the ICF before submission to the IRB.

The ICF must include a statement that the Sponsor or designee and regulatory authorities have direct access to participant records. Prior to the beginning of the study, the Investigator must have the IRB's written approval/favorable opinion of the written ICF and any other information to be provided to the participants.

Before being enrolled in the clinical study, participants must consent to participate after the nature, scope, and possible consequences of the study have been explained in a form understandable to them.

An ICF that includes both information about the study and the consent form will be prepared and given to the participant. This document will contain all the elements required by the ICH E6 Guideline for Good Clinical Practice and any additional elements required by local regulations. The document must be in a language understandable to the participant and must specify who informed the participant. Where required by local law, the person who informs the participant must be a physician.

A copy of the signed and dated consent document must be given to the participant. The original signed and dated consent document will be retained by the Investigator.

The Investigator will not undertake any measures specifically required only for the clinical study until valid consent has been obtained.

10.4 Participant Confidentiality

Participant names will not be supplied to the Sponsor. Only the participant number will be recorded in the eCRF, and if the participant name appears on any other document (e.g., laboratory report), it must be obliterated on the copy of the document to be supplied to the Sponsor. Study findings stored on a computer will be stored in accordance with local data protection laws. The participants will be informed that representatives of the Sponsor, IRB, or regulatory authorities may inspect their medical records to verify the information collected, and that all personal information made available for inspection will be handled in strictest confidence and in accordance with local data protection laws.

Applicable data privacy laws and regulations must be adhered to. The Investigator and the Sponsor are responsible for ensuring that sensitive information is handled in accordance with local requirements (e.g., Health Insurance Portability and Accountability Act [HIPAA]). Appropriate consent and authorizations for use and disclosure and/or transfer (if applicable) of protected information must be obtained.

Confidential Page 320 of 331

